5.3 Key Definitions

Baseline:

Unless stated otherwise, baseline will be defined for each subject and will be defined as the last non-analy measurement (including repeated and unscheduled assessments) obtained prior to study drug administration. Post baseline will be considered as all measurements collected after study drug administration. “Unknown”, “Not Done”, “Not Applicable” and other classifications of missing data will not be considered when calculating baseline observations unless the finding is a valid categorical observation.

Study Day:

Study day will be calculated using first study drug administration date as the reference date. If the date of interest occurs on or after the first study drug administration date, study day will be calculated as (date of interest – first study drug administration date) + 1. If the date of interest occurs prior to the first study drug administration date, study day will be calculated as (date of interest – first study drug administration date). There will be no study day 0.

Prior and Concomitant Medication:

All medications taken by subjects after screening and through to dosing will be documented as prior medications. All medications taken by subjects after dosing through to the last study day will be documented as concomitant medications.

5.4 Missing Data

There will be no imputation for missing data, unless otherwise specified. Missing data shall be presented in subject listings as either “-” (unknown or not evaluated) or “N/A” (not applicable), with the corresponding definition in the footnotes. Missing descriptive statistics, or probability values (p-values), which cannot be estimated shall be presented as “-”.

For inclusion in concomitant medication and AE tables, incomplete start and stop dates on the eCRF will be imputed as follows:

- If the stop date is incomplete, the following rules will be applied:
 - Missing day: Assume the last day of the month
 - Missing day and month: Assume the last day of the year
 - Missing day, month, and year: Assume that the event/medication is continuing
 - In the case of the death of a subject, and if the imputed end date is after the date of death, the end date will be imputed as the date of death
- If the stop date is incomplete, imputed end date will be used instead of reported end date.

This document is confidential.

- If the start date is incomplete, the following rules will be applied:
 - Missing day: Assume the first day of the month; however, if the partial date and the date of first study drug administration lie within the same month and year and the date of first study drug administration is not after the stop date of the event/medication, set to the date of study drug administration. Otherwise, set to the stop date of the event/medication.
 - Missing day and month: Assume January 1st; however, if the partial date and the date of first study drug administration lie within the same year and the date of first study drug administration is not after the stop date of the event/medication, set to the date of first study drug administration. Otherwise, set to the stop date of the event/medication.
 - Missing day, month, and year: Assume date of first study drug administration if it is not after the stop date for the event/medication. Otherwise, set to the stop date for the event/medication.

In the case of withdrawal of consent, all data from subjects who withdraw from the study will be included in all summaries up to the time of withdrawal. For all other withdrawals, all data captured will be included in the safety summaries.

For PK analysis, only observed concentration data will be used in the data analysis except for concentration values below the lower limit of quantification (BLQ). No attempt will be made to extrapolate or interpolate estimates for missing data.

6. Study Population

6.1 Subject Disposition

The number of subjects who were enrolled, who were dosed, who completed the study, and who were discontinued (post dose) from the study, along with reasons for discontinuation, will be summarized. The data will be presented by treatment and overall (frequency and the percentage of subjects) and presented by subject in a data listing.

6.2 Protocol Deviations

Subject data will be examined for evidence of protocol deviations. All protocol deviations will be categorized and presented by subject in a data listing.

6.3 Inclusion and Exclusion Criteria

All recorded inclusion and exclusion criteria status will be presented by subject in a data listing. Subjects who were screen-failed will not include in this listing. Each subject's inclusion or exclusion from each analysis population will also be presented in a data listing.

6.4 Demographics and Other Baseline Characteristics

All demographics and baseline body measurements will be summarized by treatment and presented by subject in a data listing.

This document is confidential.

Descriptive statistics (n, mean, SD, min, median, and max) will be calculated for continuous variables using the last results obtained prior to study drug administration. Frequency counts and percentages will be tabulated for categorical and binary variables.

6.5 Medical History

Medical history will be presented by subject in a data listing. The latest version of the Medical Dictionary for Regulatory Activities (MedDRA) will be used to classify medical history terms by system organ class (SOC) and preferred term (PT). Output data will include the MedDRA version 26.1.

6.6 Medications

Prior and concomitant medications will be presented by subject in a data listing. The latest version of the World Health Organization Global Drug Dictionary (WHODrug) will be used to classify medications by anatomical therapeutic chemical (ATC) classification code (2nd level) and preferred name. When 2nd level classification code is not available, 1st level classification will be used instead. Output data will include the WHODrug version used in the study.

Concomitant medications will be summarized by treatment and overall (frequency and the percentage of subjects). This summary will include the percentage of subjects with at least one concomitant medication.

6.7 Drug, and Alcohol Screens

The results of drug, and alcohol screens will be presented by subject in data listings.

6.8 Pregnancy Screening and FSH Testing

Pregnancy tests will be administered to females. The follicle stimulating hormone (FSH) level will be tested in postmenopausal females. All results will be presented by subject in data listings.

6.9 Additional Screening Tests

The results of serology tests will be presented by subject in data listings.

7. Pharmacokinetic (PK) Analyses

Phoenix® WinNonlin® software version 8.3.4 (Certara USA, Inc., Princeton, NJ) will be used for all PK analyses. Statistical analyses will be performed using SAS® for Windows, Release 9.4 (SAS® Institute Inc., Cary, NC, USA). Bioanalysis of all samples should be completed prior to the initiation of the PK and statistical analyses.

All PK concentration and PK parameter analyses will be conducted on the PK concentration population and PK parameter population, respectively.

PK concentrations will be listed and summarized by treatment, analyte, and nominal sampling timepoint using descriptive statistics (n, mean, SD, CV%, min, max, and median). Individual and mean (\pm SD) concentration versus time curves will be presented for both linear and semi-log scale by treatment.

This document is confidential.

7.1 Data Presentation

For all PK analyses, concentration values BLQ that occur before the first measurable concentration of the study drug will be set to “0.00”; BLQ values that occur after first measurable concentration will be set to “missing”. No imputations will be made on BLQ concentrations.

Invalid concentration values (due to bioanalytical or clinical issue) that occur prior to dosing will be replaced by “0.00”. Invalid concentration values that occur after dosing will be set to “missing” for tabulation, graphical representation, and calculation purposes.

The actual clock time for dosing and the actual clock time for each PK sample collection will be recorded. For all sampling times, the actual sampling duration will be calculated as the difference between the sample collection actual clock time and the actual clock time of dosing. The actual post-dose sampling times, expressed in hours and rounded off to three decimal places, will be used to calculate the PK parameters. Pre-dose sampling times will always be reported as zero (0.000), regardless of the time difference. Nominal sampling times will be used in concentration tables and mean graphs, while actual sampling times for post-dose samples will be used in the individual graphs. Actual sampling times for post-dose samples also will be used for PK parameter derivation, unless the actual sampling time is missing, in which case, the nominal time will be used.

7.3 PK Parameters

All PK parameters will be presented in data listings and summarized by treatment and analyte using descriptive statistics (n, arithmetic and geometric means, SD, CV%, min, max, and median).

The PK parameters shown in [Table 8.3-1](#), below, will be calculated by standard non-compartmental methods.

Table 8.3-1: PK Parameters

Parameter	Definition
AUC _{0-last}	area under the concentration-time curve from time zero until the last observed concentration
AUC _{0-inf}	area under the concentration-time curve from time zero to infinity (extrapolated)
Residual area	Percentage of AUC _{0-inf} due to extrapolation from the time of the last observed concentration to infinity, calculated as $[1 - (AUC_{0-t} / AUC_{0-inf})] \times 100$
C _{max}	maximum observed concentration
T _{max}	time when the C _{max} is observed
T _{1/2 el}	terminal elimination half-life, calculated as $\ln(2)/K_{el}$
K _{el}	Terminal elimination rate constant

This document is confidential.

Area under the concentration-time curve (AUC) parameters will be calculated using the linear up log down trapezoidal method, where the linear trapezoidal rule is used any time the concentration data are increasing, and the logarithmic trapezoidal rule is used any time that the concentration data are decreasing.

K_{el} will be the negative of the estimated slope of the linear regression of the ln-transformed plasma concentration versus time profile in the terminal elimination Phase. The best fit method will be used to calculate the K_{el} from at least three concentration data points, excluding C_{max} . R^2 adjusted, the goodness of fit statistic for the terminal elimination Phase, adjusted for the number of points used in the estimation of K_{el} must be ≥ 0.8 . If the $R^2 < 0.8$, the PK parameters derived from K_{el} will be presented in listing(s) but excluded from descriptive statistics in tables. The timepoint where ln-linear K_{el} calculation begins (K_{el} Lower), the actual sampling time of the last measurable concentration used to estimate the K_{el} (K_{el} Upper), and the R^2 adjusted for the ln-linear regression for the calculation of the elimination rate constant will be reported.

If the Residual area is more than 20%, all the derived parameters depending on $AUC_{0-\infty}$ (i.e., $AUC_{0-\infty}$) will be flagged accordingly.

7.4 PK Comparison Between Formulation A Versus Formulation B

For the PK comparison of the relative bioavailability between formulation A and formulation B, an ANOVA model will be used to compare the log transformed PK parameters AUC_{0-last} , $AUC_{0-\infty}$, and C_{max} . The estimated ratio (B/A) of model -adjusted geometric means will be used to perform this comparison. To estimate the geometric mean ratio, a linear mixed effects model will be used to the data. The response variable will be the natural log transformed PK parameter, and the model will include treatment as fixed effect and subject as random effect. The model will be fit using restricted maximum likelihood, and the Kenward--Roger degrees of freedom approximation. From this model, the adjusted means will be estimated for each treatment (A and B). The difference in geometric means will be estimated, accompanied by the corresponding two one-sided 90% confidence interval (CI). The estimates and CIs will be exponentiated using base e in order to estimate the geometric mean ratio and associated two one-sided 90% CI..

The SAS code for the analysis model for ANOVA will follow the format given below (using the Mixed Procedure to fit the linear regression). The input variables, datasets, and labels are depicted in italicized red text and have been given generic names.

```
proc mixed data= dataset;  
  class subject treatment;  
  model ln_PK_parameter = treatment / ddfm= kr solution;  
  random subject;  
  lsmeans treatment;  
  estimate 'formualtion A vs Formulation B' treatment 1 -1/c1 alpha=0.1;  
run;
```

This document is confidential.

8. Immunogenicity Analysis

Anti-AIO-001 antibodies will be evaluated in serum samples collected before and after dosing at 168 hours, 336 hours, 504 hours, 672 hours, 1344 hours, 2016 hours, 3360 hours, and 4032 hours post-dose. The results will be presented in a data listing by subject.

A subject with any ADA is defined as subject with at least one baseline or post-baseline ADA-positive sample. A pre-existing ADA subject is defined as subject who has a baseline ADA-positive sample. ADA-negative subject is defined as subject without treatment-induced or treatment-boosted ADA-positive sample during the treatment or follow-up observation period. ADA-positive subject is defined as subject with at least one treatment-induced or treatment-boosted ADA-positive sample at any time during the treatment or follow-up observation period. Treatment-induced ADA-positive is defined as subject who has baseline ADA-negative sample and at least one post-baseline ADA-positive sample, while treatment-boosted ADA positive is defined as subject who has both baseline and post-baseline ADA-positive samples, and the titer of the post-baseline sample is equal to or more than 4-fold of the baseline titer.

The frequency and percentage of the following information will be summarized; subjects with any ADA, pre-existing ADA subjects, ADA-positive subjects and ADA-negative subject.

All immunogenicity analyses will be conducted on the immunogenicity population.

The frequency and percentage of ADA results will be summarized by treatment and overall.

In addition, the adverse event overview by subject with ADA status will be presented

9. Safety

Safety and tolerability analysis will be performed for all subjects in the safety population. No inferential statistical analysis of safety data is planned.

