1.2 Timings of Analyses

Interim Analysis

An interim analysis will be performed at the end of 12 weeks, after all subjects complete Day 85, safety, tolerability, pharmacokinetic (PK), and immunogenicity data will be analyzed for primary and secondary endpoints for an interim report

Final Analysis

The final safety, tolerability, PK, and immunogenicity analysis will be completed after all subjects complete the final study visit or terminate early from the study.

This document is confidential.

2. Study Objectives

- Primary objective:
 - To compare the safety and tolerability of 400 mg of AIO-001 as the new formulation (Formulation B) with a 400 mg dose of AIO-001 administered as the original formulation (Formulation A) in healthy volunteers.
- Secondary Objectives:
 - To evaluate the PK of a single subcutaneous (SC) AIO-001 dose of Formulation A in healthy volunteers.
 - To evaluate the PK of a single SC AIO-001 dose of Formulation B in healthy volunteers.
 - To evaluate the immunogenicity of AIO-001 in healthy volunteers.

3. Study Description

This is an open-label single dose, parallel group, 24-weeks, Phase 1 study in 16 healthy subjects.

The study is designed to evaluate and compare the safety, tolerability, PK, and immunogenicity of SC AIO-001 400 mg using two different formulations (original Formulation A and new Formulation B) in 16 healthy volunteers (8 receiving each formulation).

Subject Selection

Up to approximately 16 healthy adult males or females aged 18 to 55 years, with body mass index (BMI) >18.5 and <32.0 kg/m², non-smokers, will be enrolled in this study.

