3.3 Randomization

Randomization schemes will be generated using SAS® for Windows software, prior to study execution.

Subjects will be randomized prior to dosing, after confirming continued eligibility. Subjects eligible for participation will be randomized to receive formulation A or formulation B in a 1:1 ratio, for a total of 8 subjects receiving formulation A and 8 subjects receiving formulation B.

The study will include 2 sentinel subjects (1 for each treatment) dosed initially, and the remaining 14 subjects dosed no sooner than 24 hours.

Each subject will be randomly assigned a 4-digit randomization number beginning with “1”. Each randomization number corresponds to a treatment assignment on the randomization scheme. Sentinel subjects will be assigned to the first 2 randomization numbers (i.e., 1001, 1002).

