3.5 Subject Withdrawal and Replacement

Subjects will be advised that they are free to withdraw from the study at any time. Over the course of the study, the Sponsor and the Investigator or designee may withdraw any subject from the study for one of the reasons described below; subject withdrawal will be done in accordance with the local guidance at the clinical site:

- Safety reason;
- Non-compliance with protocol requirements;
- Significant protocol deviation;
- Positive pregnancy test, drug screen or alcohol breath test.

Subjects who withdraw prior to dosing may be replaced automatically. In the event that the number of dropouts exceeds initial expectations, subjects who withdraw or are withdrawn from the study after dosing, for reasons other than safety and tolerability, may be replaced after consultation between the Investigator and the Sponsor. In such case, the total number of subjects dosed will remain within a maximum of 10 subjects for groups A and B.

4. Endpoints

- Primary Endpoints:
 - Adverse events (AEs), vital sign measurements (blood pressure, heart rate, respiratory rate, and tympanic temperature), 12-lead electrocardiogram (ECG) recordings, physical examinations, and clinical laboratory test results, including hematology, biochemistry, and urinalysis.
- Secondary Endpoints:
 - PK endpoints may include but are not limited to AIO-001 concentrations, AUC_{0-last}, AUC_{0-inf}, C_{max}, T_{max}, T_{1/2}.

This document is confidential.

- Incidence of anti-drug antibody (ADA) to AIO-001.

Analysis Populations

All subjects' inclusion status into each analysis population will be determined after database lock. Subjects will be analyzed according to the treatment received.

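### Does the random subject effect in SAP 7.4, with only one PK value per subject, undermine the formulation ratio or its 90% CI?

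*SAP*

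**What the plan says.** SAP 7.4 opens by saying that "an ANOVA model will be used to compare the log transformed PK parameters". It goes on to say that "a linear mixed effects model will be used to the data" and that "the model will include treatment as fixed effect and subject as random effect", fitted by restricted maximum likelihood with Kenward–Roger degrees of freedom. The SAS block is described as "using the Mixed Procedure to fit the linear regression" and contains the statement "random subject". The outputs requested are the adjusted means, the B/A ratio of geometric means and its 90% confidence interval. Variance components are not among them.

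On the design, SAP Section 3 says: "This is an open-label single dose, parallel group, 24-weeks, Phase 1 study in 16 healthy subjects". SAP 3.3 allocates 1:1, "for a total of 8 subjects receiving formulation A and 8 subjects receiving formulation B". SAP 7.2 schedules 19 blood samples per subject, but SAP 7.3 reduces these by non-compartmental analysis to single parameters before the model of 7.4 is applied. SAP 3.5 allows replacements, with the limit that "the total number of subjects dosed will remain within a maximum of 10 subjects for groups A and B". A replacement is a new subject, so this gives nobody a second record.

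**The concern.** A random subject effect belongs in a crossover or replicate design, where each subject contributes several values. Here each subject contributes one value per parameter, so the model asks for two variances where the data inform only one. The REML information for the two variances is singular. The worry is that the prespecified code might fail, or that its Kenward–Roger correction, which uses that information matrix, might return wrong df and hence a wrong interval. Section 7.4 is the only planned inferential comparison of the formulations, because safety is descriptive (SAP Section 9), so a faulty interval there would matter. The three labels for one analysis (ANOVA, mixed model, regression) add to the impression that the model was not thought through.

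**Working it through.** The SAP gives no figure to reproduce: SAP 3.1 reports no formal sample size calculation, and neither document gives an SD. The check is therefore whether the random term changes any requested output.

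**Inputs.** 8 subjects per arm, N = 16 (SAP 3.3); one ln-transformed value per subject per parameter (SAP 7.3 and 7.4); treatment as the only fixed effect; alpha 0.1 for a 90% CI (SAP 7.4 code).

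**1. Covariance.** Write s²_b for the subject variance and s²_e for the residual variance. With one record per subject the random-effect design matrix is the identity, so V = s²_b·I + s²_e·I = (s²_b + s²_e)·I = s²·I. Only s² enters the likelihood.

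**2. Information.** Each entry of the 2 × 2 REML expected information for (s²_b, s²_e) is (N − 2)/(2s⁴). At s² = 1 that is 14/2 = 7.0 in all four cells: rank 1, determinant 0. The split between the two variances is not identifiable.

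**3. Ratio and standard error.** Because V is proportional to I, generalised least squares equals ordinary least squares. The log ratio is the difference between the two arm means, and SE = √[s²(1/8 + 1/8)] = s/2. Neither depends on the split.

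**4. Kenward–Roger.** The small-sample inflation of the SE is built from Q_ij − P_i Φ P_j. Here both terms equal X'X/s⁶ and cancel, so the inflation is zero whatever weights the singular matrix supplies. For the df, the variance of the contrast is s²/4, with gradient (1/4, 1/4) in the two variances. That gradient lies in the column space of the information matrix, so every generalised inverse gives the same answer: df = 2(s²/4)² / [(1/16)(s⁴/7)] = (s⁴/8) / (s⁴/112) = 14.

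**5. Interval.** With t(0.95, 14) = 1.761, the half-width is 1.761 × s/2 = 0.881 s. This is exactly the equal-variance two-sample result. The same holds at other sizes:

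| Subjects per arm | df | t | 90% half-width (log scale, in SD) |
|---|---|---|---|
| 6 | 10 | 1.812 | 1.046 |
| 7 | 12 | 1.782 | 0.953 |
| 8 | 14 | 1.761 | 0.881 |
| 10 | 18 | 1.734 | 0.775 |

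The last row applies if the cap in SAP 3.5 means 10 per group. For scale, under assumed between-subject CVs of 20% to 50% and an observed ratio of 1, the 8 v 8 interval runs from 0.840–1.191 to 0.660–1.516, with or without the random term.

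**6. Numerical check.** One simulated 8 v 8 data set had pooled variance 0.035899. Setting the subject share of that total to 0, 10, 25, 50, 75, 90 and 99.9% gave the same REML log-likelihood each time (14.20986), the same log difference (−0.0427) and the same SE, √(0.035899 × 0.25) = 0.0947. All four information entries were 14/(2 × 0.035899²) ≈ 5432. The df stayed at 14 (13.997 to 14.001) under different generalised inverses and small perturbations of the singular matrix. Over 2,000 simulated data sets, with the subject-to-residual ratio varied from 0 to 100, the largest relative change in the SE was 4 × 10⁻¹⁶.

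**The case for a change.** The best case for a change is that a prespecified model should not rely on how software copes with a singular matrix. A random-intercept REML fit of such data in the Python package statsmodels stopped with a singular-matrix error, whereas the one-way model fitted normally with 14 df. The SAP names no fallback, so the analyst might have to alter the model after seeing the data. If variance components were printed, the residual estimate alone could move 101-fold at equal likelihood (a ratio of 0 against 100), and a reader might take it for within-subject variability, which this design cannot estimate.

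The algebra stands: the split is unidentifiable and the random statement is redundant. The consequence does not. The failure was in statsmodels; the PROC MIXED code that the SAP specifies was not run, and no wrong interval has been shown. An analyst who met an error or warning would drop the redundant term and arrive at the ANOVA named in the section's first sentence. That leaves no room for a data-driven choice, because every route that yields an answer yields the same ratio, SE and df. The 101-fold range concerns a quantity that the section does not ask to be reported. As for the three labels, a one-way ANOVA is a regression on a treatment indicator, and PROC MIXED can fit it; only the mixed-model label is out of place.

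The sign of the ESTIMATE contrast against the B/A ratio in the text is a separate question, which this point does not settle.

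**Conclusion.** No change to the plan follows. The random subject term looks like a carry-over from a repeated-measures template, and deleting it would be tidier. With one value per subject it leaves the geometric mean ratio, its standard error, the df (subjects in the model minus 2) and the 90% CI exactly as a one-way ANOVA gives them, so the gain in any requested result is zero. The stakes are also low: PK is secondary, SAP 7.4 sets no margin, and no decision is tied to the interval.

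This rests on each subject contributing one value per parameter, which the single-dose parallel design ensures, and on the fit either resolving or being replaced by the same model without the redundant term. How SAS handles the singular fit was not tested. SAP Section 1 already provides for changes made after finalisation to be documented in the clinical study report, so dropping the term could be recorded there.

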5.1 General Methods

SAS for Windows software will be used to perform all statistical analyses. All data in the database will be presented in the data listings. Unless otherwise stated, all listings will be sorted by treatment, subject number, and assessment date/time.

The following labels for treatment will be used on all tabulations where the results are displayed by treatment, in the following order:

- 400 mg of 100 mg/ml AIO-001 Formulation A

This document is confidential.

- 400 mg of 182 mg/ml AIO-001 Formulation B

5.2 Summary Statistics:

Unless otherwise stated, continuous variables will be summarized using the number of observations (n), and the statistics mean, median, standard deviation (SD), minimum (min) and maximum (max). The min and max values will be presented to the same number of decimal places as recorded in the eCRF, mean and median will be presented to one more decimal place than the raw data, and the SD will be presented to two more decimal places than the raw data.

Summaries of change from baseline variables will include only subjects who have both a baseline value and corresponding post baseline value at the timepoint of interest. Categorical and binary variables will be summarized with frequency counts and percentages. Percentages will be rounded to one decimal place, with the denominator being the number of subjects (N) in the relevant population, unless otherwise stated.

For PK data, values will be rounded to two decimal places in the listings and tables, except for the following situations:

- Terminal elimination rate constant (K_{el}) and R-squared (R^2) adjusted data shall be rounded off to four decimal places.
- PK parameters related to time, such as T_{max} , lower terminal elimination rate constant (K_{el_Lower}), and upper terminal elimination rate constant (K_{el_Upper}), must be reported with the same precision as the actual sampling time, rounded to three decimal places.
- Concentration versus time data, as well as C_{max} shall be reported as they appear in the corresponding dataset.
- Summary statistics, including geometric mean and coefficient of variation (CV%), will be presented to the number of decimal places is contingent on the number of places in the raw data plus one additional decimal place. The geometric mean and CV% will not be calculated for T_{max} , $T_{1/2}$, and K_{el} .

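### SAP 7.4 defines the formulation comparison as B/A, but its SAS contrast gives A/B when Formulation A is the first class level

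*SAP*

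**What the plan says.** SAP section 7.4 sets the direction in its text: "The estimated ratio (B/A) of model -adjusted geometric means will be used to perform this comparison". It also says how the log-scale result is converted: "The estimates and CIs will be exponentiated using base e in order to estimate the geometric mean ratio". No sign change or reciprocal is mentioned.

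The section then gives a PROC MIXED template, introduced by "The SAS code for the analysis model for ANOVA will follow the format given below". The two lines that matter are the class statement, "class subject treatment", which carries no ordering option, and the contrast, "estimate 'formualtion A vs Formulation B' treatment 1 -1/c1 alpha=0.1". On what may be replaced in the template, the SAP says: "The input variables, datasets, and labels are depicted in italicized red text and have been given generic names".

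The coding of the treatment variable is not stated. SAP section 5.1 gives the treatment labels for tabulations, in this order: "400 mg of 100 mg/ml AIO-001 Formulation A" and "400 mg of 182 mg/ml AIO-001 Formulation B". SAP section 11.2.4 also puts Treatment A before Treatment B in tables and listings.

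**The concern.** The ESTIMATE coefficients apply to the class levels in their sorted order. If A sorts first, coefficients of 1 and -1 give A minus B on the log scale, so the exponentiated result is A/B. The text asks for B/A.

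This is the only inferential comparison of the two formulations in the plan, because SAP section 9 limits safety to descriptive analysis. Protocol section 1.4 says the new formulation is meant for a proposed phase 2 trial, so whether it gives higher or lower exposure than the original is what a reader will take from this analysis. A programmer who follows the template, and an author who follows the text, could between them report the reciprocal of the intended ratio. SAP section 1.2 plans PK analyses after Day 85 and again at the end of the study, so the line may be run more than once.

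**Working it through.** The documents give no expected ratio, variability or power for this comparison, and SAP section 3.1 says that no formal sample size calculation was done. There is therefore no planned figure to reproduce. The check covers the class order, the algebra of the contrast, and one illustration.

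**1. Class order.** With no ordering option, PROC MIXED sorts levels by formatted value. Sorting the two SAP 5.1 labels puts the 100 mg/ml label (Formulation A) before the 182 mg/ml label (Formulation B). Plain codes A and B also sort A first.

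**2. Algebra.** Let a and b be the adjusted log-scale means for A and B.

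- Levels ordered A, B with coefficients (1, -1): the estimate is a − b, and exp(a − b) = A/B.
- Levels ordered A, B with coefficients (-1, 1): the estimate is b − a, and exp(b − a) = B/A.

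So for any B/A estimate r with limits L and U, the printed contrast gives 1/r with limits 1/U and 1/L. This holds whatever the data.

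**3. The other order.** If B were coded to sort first, (1, -1) would give B/A, but the line as written would print it under an A vs B label. Under neither order does the line as written give a B/A value with a B/A label.

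**4. Illustration.** Inputs: 8 per arm (SAP section 3.3) and alpha = 0.1 (the template). Assumed, because the documents give neither: observed B/A = 0.80 and CV = 30%. The calculation uses a one-way two-group model with 8 + 8 − 2 = 14 df.

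- SD on the log scale = sqrt(ln(1 + 0.30²)) = 0.2936
- SE of the difference = 0.2936 × sqrt(2/8) = 0.1468
- t(0.95, 14 df) = 1.7613, so the half-width = 1.7613 × 0.1468 = 0.2585
- ln(0.80) = −0.2231
- B/A: exp(−0.2231) = 0.800, limits exp(−0.2231 ± 0.2585) = 0.618 to 1.036
- A/B, from the printed contrast with A first: exp(0.2231) = 1.250, limits exp(0.2231 ± 0.2585) = 0.965 to 1.619

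The same assumed ratio over a range of CV:

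| Assumed CV | B/A, as the text defines it | A/B, from the printed contrast with A first |
|---|---|---|
| 20% | 0.80 (0.672 to 0.952) | 1.25 (1.050 to 1.488) |
| 30% | 0.80 (0.618 to 1.036) | 1.25 (0.965 to 1.619) |
| 40% | 0.80 (0.570 to 1.123) | 1.25 (0.890 to 1.755) |

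**5. What does not change.** At CV 30%, |t| = 0.2231/0.1468 = 1.52 on 14 df (p = 0.151) in both directions, and the ratio of upper to lower limit is 1.68 in both.

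**6. Numerical check.** In a simulated two-group data set with 8 per arm, contrast (1, -1) exponentiated to 0.8545, equal to the geometric mean of A over that of B. Contrast (-1, 1) gave 1.1703, which is B over A.

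**The case against.** The strongest reply is that the code is only a template. The SAP calls labels generic, so the A vs B label may be a placeholder. The colour and italics that marked the generic items are lost in the text available here, so we cannot see which tokens were marked. The section heading also says A versus B directly above a text that defines B/A, so the phrase may name the comparison without fixing its direction. On this reading only the text sets a direction, and the code's direction depends on a class order that the SAP leaves open.

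This weakens the argument from the label, but not the argument from the coefficients. The SAP's sentence on generic items names variables, datasets and labels, not coefficients, and with A first, 1 and -1 give A/B whatever the label says.

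A second reply is that a swap would be noticed. The same template requests LS means by treatment, SAP section 7.3 requires geometric means by treatment, and SAP section 12 puts programs through quality control. The table shells, which are in a separate document not available for this review, may show the intended direction. All of this stands, and it lowers the chance of a misreported result. It does not make the code agree with the text.

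A third reply is that little depends on it. A/B carries the same information as B/A, no equivalence limits or decision rule exist, and the PK objectives are secondary. That also stands, and it is why the point ranks no higher than something that should be fixed.

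Finally, the interval above comes from a one-way fit and is not output from the SAP's model, which adds a random subject effect and Kenward-Roger degrees of freedom. With one value per subject for each parameter, that effect cannot be separated from the residual. The interval is an illustration; the reciprocal relation does not depend on it.

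**Conclusion.** The concern holds and should be fixed. With Formulation A as the first class level, which is the default for the SAP's own labels, the printed contrast, exponentiated as the text directs, gives A/B and not the B/A ratio that section 7.4 defines. The size of the discrepancy is exact: the reciprocal of the estimate, with the limits inverted and swapped. The figures of 0.80 and 1.25 rest on an assumed ratio and an assumed CV; the reversal does not.

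The consequence is conditional. With A first, a row labelled A vs B is correct as it stands. The result is misdirected only if that row is reported as B/A. No power, test result or decision rule changes.

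**What to change.** In SAP section 7.4:

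- State the treatment coding and class order, with Formulation A first and Formulation B second.
- Change the contrast to `treatment -1 1` and label it Formulation B vs Formulation A.
- State that the log-scale LS-mean difference, B minus A, and its two-sided 90% CI are exponentiated to give B/A. Two-sided 90% describes the interval that `alpha=0.1` already requests, so the confidence level does not change.

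Check that the table shells use the same direction. The cost is one code line and two sentences in the SAP, with no new data.
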